4.2 OTHER ENDPOINTS

4.2.1 QUESTIONNAIRE RESPONSES OF EACH STEP IN THE LIPIFLOW TREATMENT PROCEDURE WITH ACTIVATOR LFD-2100

For questions with a 'Yes' or 'No' responses, the frequency and proportion of each question with response 'Yes' will be reported. For questions with five levels of rating score responses, the frequency and proportion of each level of rating score responses will be tabulated. The mean and median of rating score of each question will also be reported. List of eyes with a rating score of 1 or 2 on a question and the corresponding comment will be provided.

4.2.2 OCULAR SURFACE STAINING

Corneal staining will be evaluated in five corneal regions on a scale of 0 (none), 1 (mild), 2 (moderate) and 3 (severe). The total corneal staining grade will be calculated as the sum of the grades for each of the five corneal regions on a scale from 0 to 15. A lower grade indicates less corneal surface desiccation. Conjunctival staining will be evaluated in six conjunctival regions on a scale of 0 (none), 1 (mild), 2 (moderate) and 3 (severe). The total conjunctival staining grade will be calculated as the sum of the grades for each of the six conjunctival regions on a scale from 0 to 18. A lower grade indicates less conjunctival surface desiccation. Mean ocular surface stain grade score will be reported at pre-treatment visit and treatment visit. Change in ocular surface stain grade score (treatment minus pre-treatment) will be summarized.

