Typical duration of study exams and treatment will last approximately 1-2 hours. All data will be de-identified or encoded to protect the privacy of the subject and confidentiality of the data. Although the study is not masked, to maintain consistency, it is recommended that a single individual (study technician or coordinator designated by the investigator) conduct all study-related eye testing, although a back-up person should also be designated and trained.

The investigators will be provided with the LipiFlow Consoles (if needed), LipiFlow Activator LFD-2100, Semi-permanent Cable, Lid Stabilizer Tape, and the LipiFlow, Activator, and Cable Instructions for Use (IFU), including the Quick Start Guide. Prior to human use, Activator LFD-2100 will be described in sufficient details in a Clinical Investigator Brochure to adequately describe the theory of operation and compliance to applicable standards in humans.

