3.1. Disconnect Activator LFD-2100 from subject's eyes

3.2. Disconnect Activator LFD-2100 from the Cables

After completion of each treatment, the treatment reports automatically generated by LipiFlow Console will be printed out and collected. The reports will show completion of the treatment and additionally the changes of pressure and temperature during the treatment.

Following the completion of LipiFlow treatment, the Investigator or designee will perform a slit-lamp evaluation (**Appendix D**) and ocular surface staining (**Appendix F**) in each eye to check for any adverse events.

Questionnaire

A questionnaire will be administered to the investigator or designee to collect information regarding the clinical use of Activator LFD-2100 (**Appendix A**).

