2.2 DATA CONVENTIONS

Descriptive statistics will typically include sample size (N), mean, standard deviation (SD), median, minimum (Min.), and maximum (Max.) as appropriate for continuous variables. For categorical data, the frequency and proportion will be computed.

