APPENDIX I: TABLE LISTING

Variable	Subjects/Eyes
ENROLLMENT/PRE-TREATMENT	
Accountability/Enrollment	
Subjects by investigational site (n)	subjects
Demographics	
Demographic – Age in years (N, Mean, SD, Median, Min, Max), sex, race and ethnicity (n and %)	subjects
PRIMARY STUDY ENDPOINT	
Successful completion of LipiFlow treatment – (n, %) List of eyes with unsuccessful cases will be provided	eyes
OTHER ENDPOINTS	
Questionnaire responses of each step of LipiFlow treatment (n, %) for Yes/No or rating responses and mean and median for each rating score List of eyes with rating score of 1 or 2	eyes
Ocular surface staining at pre-treatment and treatment and the difference (N, Mean, SD, Median, Min, Max)	eyes
Meibomian glands assessment Meibomian glands secretion score at pre-treatment (if available) –(N, Mean, SD, Median, Min, Max) Proportion of utilization of meibomian gland evaluator (n,%)	eyes
Medical findings from slit lamp exam (n, %)	eyes
Ocular symptoms (n, %)	eyes
Rate of complications and adverse events (n, %)	eyes

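### Post-treatment staining is a per-eye harm check, but no planned output counts the eyes that worsened, and a new focal severe region can vanish from the summed score

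*SAP*

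**What the plan says.** **Purpose.** In Protocol 10.3, after the Activator is removed, the investigator or designee repeats the slit-lamp examination and the staining "in each eye to check for any adverse events". Protocol Appendix F has each of five corneal and six conjunctival regions graded 0 to 3 and documented.

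**Analysis.** SAP 4.2.2 works on totals only:

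- Cornea: "The total corneal staining grade will be calculated as the sum of the grades for each of the five corneal regions".
- Conjunctiva: "The total conjunctival staining grade will be calculated as the sum of the grades for each of the six conjunctival regions".
- By visit: "Mean ocular surface stain grade score will be reported at pre-treatment visit and treatment visit".
- Change: "Change in ocular surface stain grade score (treatment minus pre-treatment) will be summarized".

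The Appendix I row, to be produced by eye, is "Ocular surface staining at pre-treatment and treatment and the difference (N, Mean, SD, Median, Min, Max"). This agrees with the general convention in SAP 2.2.

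**Other harm outputs.** SAP 4.2.4 and Appendix I report the number and percentage of eyes with complications and adverse events. Appendix I does the same for slit-lamp medical findings and ocular symptoms. The SAP contains no regional staining table, no count of eyes with worse staining, and no listing of such eyes.

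**The concern.** A check made eye by eye for harm asks which eyes are worse, and how many. The planned summaries answer a different question: where the centre of the distribution of total change lies, and how far it spreads. Summing the regions loses information in two ways.

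- **Between eyes.** Improvement in some eyes offsets worsening in others in the mean. The maximum reveals that at least one eye worsened, but not how many did.
- **Within an eye.** A new severe region can be offset by small improvements in other regions of the same eye. The total does not move, and neither does any statistic computed from its change.

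At stake is how the staining result can be read in the final report. A change near zero would be compatible with no eye worse, or with a material share of eyes worse straight after contact with the device, and the tables would not let a reader tell these apart.

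**Working it through.** **Scale check against the SAP.** Cornea: 5 regions x 3 = 15. Conjunctiva: 6 regions x 3 = 18. Both stated ranges are reproduced. The documents give no expected staining values, SD or worsening rate, so the data below are constructed to show what the planned statistics can and cannot reveal. They are not predictions. The number of eyes, 50, is the protocol minimum.

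**1. A count that the planned table does not show.** Assume 10 eyes at +3, 15 at -2 and 25 at 0.

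- Mean = (10 x 3 - 15 x 2)/50 = 0
- SD = sqrt((10 x 9 + 15 x 4)/49) = sqrt(150/49) = 1.75
- Median 0, minimum -2, maximum +3

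The maximum shows that some eye worsened by 3. Nothing shows that 10/50 = 20% did.

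**2. Same mean, median, minimum and maximum, different number worse.**

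| Constructed data (50 eyes) | Eyes worse | Mean | Median | Min | Max | SD |
|---|---|---|---|---|---|---|
| 1 at +3, 3 at -1, 46 at 0 | 1 | 0 | 0 | -1 | +3 | sqrt(12/49) = 0.49 |
| 5 at +3, 15 at -1, 30 at 0 | 5 | 0 | 0 | -1 | +3 | sqrt(60/49) = 1.11 |

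Only the SD differs, and an SD cannot be converted back into a number of worsened eyes.

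**3. Offsetting within an eye.** Take corneal grades 0, 1, 1, 1, 0 before and 3, 0, 0, 0, 0 after.

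- Total before = 3 and total after = 3
- Change = +3 - 1 - 1 - 1 = 0
- Largest regional change = +3

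With five such eyes among 50 and the rest unchanged, the change has mean, SD, median, minimum and maximum all equal to 0, and the totals at the two visits are identical. A three-grade focal worsening in 5/50 = 10% of eyes is then absent from every planned staining statistic.

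**4. What a count would give.** Exact (Clopper-Pearson) two-sided 95% intervals for the proportion of eyes with worsening, for assumed counts:

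| Eyes worse | n = 50 | n = 100 |
|---|---|---|
| 0 | 0 to 7.1% | 0 to 3.6% |
| 1 | 0.05 to 10.6% | 0.03 to 5.4% |
| 5 | 3.3 to 21.8% | 1.6 to 11.3% |

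For zero events the upper limit is 1 - 0.025^(1/n). These intervals treat eyes as independent. Both eyes of each subject are treated, so 50 eyes are 25 subjects. With no subject affected, the upper limit is 1 - 0.025^(1/25) = 13.7%. That is a reason to count subjects as well as eyes.

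**The case against.** **The analysis is not a mean alone.** A reader who stops at SAP 4.2.2 might infer that worsening in one eye simply cancels against improvement in another. Appendix I does not support that. The maximum is planned, and an increase in one eye's total cannot cancel out of it. In examples 1 and 2 the printed table shows +3. This stands, and the between-eye problem is therefore limited to the missing count.

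**Harm has its own rows.** A reader might also infer that focal damage disappears from the report. The documents do not support this either. Adverse events of any severity are to be reported (Protocol 11.3). Corneal abrasion is both an anticipated adverse event (11.1) and a named slit-lamp finding (Appendix D), and both are counted by eye in the SAP. This stands for anything recorded as an event or a finding. It does not close the gap, because no staining grade or change triggers either row. Protocol 17.0 describes ocular signs as events when the investigator judges them clinically important or when they need treatment. The regional grades are the only standardised paired measure of staining, and the summary does not use them by region.

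**The within-eye case may be rare.** It needs improvement in some regions together with worsening in another, and nothing in the documents says how often that happens. This stands: the example shows what could be missed, not how much will be.

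**A regional count is sensitive to grading noise.** Assume, for illustration, a 5% chance per region of a one-grade upward error, independent across regions. An increase in any region is then flagged in 1 - 0.95^5 = 23% of corneas and 1 - 0.95^6 = 26% of conjunctivas with no true change. At 2% the figures are 10% and 11%. This stands too. It argues for a stricter threshold, and against making a one-grade count the main staining result.

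**Examiners.** Protocol 10.1 says "it is recommended that a single individual (study technician or coordinator designated by the investigator) conduct all study-related eye testing", with a trained back-up. One might infer that a single examiner ought to be mandatory. The documents give no figure for examiner variability on which to base that, and it is a separate operational choice.

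**Conclusion.** The point holds as a reporting gap in a descriptive safety output. The stated use of the examination is a per-eye check, but no planned output gives the number of eyes with worse staining, and a severe new region can be absent from every planned change statistic when other regions of the same eye improve. In the constructed data, 20% of eyes worse goes uncounted, and a three-grade focal worsening in 10% of eyes leaves all the change statistics at zero. These sizes rest on assumed data. The actual frequency is unknown.

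The documents do not support the conclusion that harm would go unreported, since the maximum, the adverse event rows and the slit-lamp rows remain. Nor do they claim that a mean change near zero shows no ocular surface effect: there is no staining hypothesis or decision rule. Staining is not among the protocol's listed endpoints (20.2), so the primary endpoint and the sample size are untouched. This is a cheap improvement worth making, not a flaw in the trial's main conclusion.

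**What to change.** In SAP 4.2.2 and Appendix I, keep the existing summaries and add the following for cornea and conjunctiva separately:

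1. A shift table of pre-treatment against post-treatment grade for each region.
2. The number and percentage of eyes, and of subjects, with worsening in any region at a threshold fixed before analysis. An example is an increase of at least 2 grades, or an increase to grade 3. The documents give no threshold, so this is an analysis choice. It is stricter than a one-grade rise and so less exposed to grading noise. It would be a reporting cut-off, not a definition of an adverse event.
3. A listing of those eyes, in the style already planned for unsuccessful treatments (SAP 4.1) and for ratings of 1 or 2 (SAP 4.2.1).

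Present the count as descriptive. With no control arm, some eyes will be flagged through grading variability alone.

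The cost is a few extra tables and one listing. The regional grades are already documented under Protocol Appendix F, so no new data, visits or subjects are needed.

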4.2.3 MEIBOMIAN GLANDS ASSESSMENT

Summary statistics of total meibomian glands secretion score will be reported at pre-treatment visit if data is available. The proportion of utilization of meibomian gland evaluator will be provided.

4.2.4 RATE OF COMPLICATIONS AND ADVERSE EVENTS

The frequency and proportion of eyes with complications and adverse events will be reported throughout the study.

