1. SYNOPSIS

- PROTOCOL:** Evaluation of the LipiFlow System with a New Activator (Model LFD-2100)
- Protocol Number: DRYE-105-ACTS
- STUDY TREATMENTS:** Investigational Product: The new Activator (Model LFD-2100).
- STUDY OBJECTIVE:** The purpose of this study is to confirm the clinical use of the LipiFlow system with Activator LFD-2100 to successfully complete LipiFlow treatment procedure in human subjects. Additionally, the investigator rating of the ease of use of the LipiFlow system with Activator LFD-2100 will be obtained.
- CLINICAL HYPOTHESIS:** The Activator Model LFD-2100 will provide successful LipiFlow treatments in 95% or more cases.
- OVERALL STUDY DESIGN:**
- Structure:** Prospective, open-label clinical study.
- Number of sites:** Three (3) to 5 investigators in up to 4 sites in the USA.
- Duration:** A pre-treatment visit and a treatment visit (may happen on the same day)
- Administration:** Minimum 50 eyes and up to 100 eyes will be treated in this study. The investigators or designees will perform LipiFlow treatment with the Activators LFD-2100 on both eyes. The Investigator or designee will complete a questionnaire regarding the clinical use of Activator LFD-2100. The treatment reports automatically generated by LipiFlow Console after completion of each treatment will be collected.
- Visit Schedule:** Each subject will have 1-2 visits which include informed consent, screening for study participation, and receiving the LipiFlow treatment. A questionnaire will be completed by the investigator or designee. A typical pre-treatment visit will be approximately 30-60 minutes long, and a typical treatment visit will take another 30-60 minutes.

STUDY POPULATION CHARACTERISTICS:

Condition: Adults with bilateral meibomian gland dysfunction (MGD) (refer to inclusion/exclusion criteria for requirements).

Number of Subjects/Eyes: Minimum 50 eyes and up to 100 eyes to be treated.

Each research subject must meet the following inclusion/exclusion criteria in order to participate in this study:

Inclusion Criteria (all criteria apply to each study eye):

To be able to participate in this study, subjects must:

- Be at least 22 years old.
- Has been diagnosed as bilateral MGD prior to the study visit, or has evidence of MGD in both eyes. NOTE: MGD diagnosis can be based on prior medical records, investigator opinion or based on assessment of meibomian glands of the lower eyelid (see Appendix E).

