- Availability, willingness, ability and sufficient cognitive awareness to comply with study protocol, examination procedures and visit.
- Be willing to provide informed consent and authorization to disclose protected health information or equivalent documentation necessary to comply with applicable privacy laws pertaining to medical procedures.
- Ability to understand and respond in English.

Exclusion Criteria (all criteria apply to each study eye):

Subject will not be able to be in the study, if the subject:

- Has a history of certain medical conditions that have been identified as contraindications and precautions of the LipiFlow System (refer to the *LipiFlow Thermal Pulsation System Instructions for Use* for details)
- Has a history of prior eye surgery or trauma, active eye disease, or other eye abnormality in the study eye(s), which in the opinion of the investigator would confound the study results.
- Is pregnant, or is breast feeding.
- Concurrent participation or expected participation in an interventional (i.e., surgical or pharmaceutical interventional) clinical trial within 14 days prior to study screening.

STUDY ENDPOINTS:*Primary Endpoint:*

- Successful completion of LipiFlow treatment with Activator LFD-2100 in 95% or more cases.

Other Endpoints:

- Questionnaire rating of each step in the LipiFlow treatment procedure with Activator LFD-2100.
- Rate of adverse events and complications.

STUDY VISITS AND PROCEDURES:

Inclusion and exclusion qualifications will be assessed at the enrollment visit according to the inclusion/exclusion criteria.

The Informed Consent Document and Authorization for Use/Disclosure of Health Information form to comply with US Health Information Portability and Accountability Act (HIPAA) must be signed by any subjects who agree to participate in the study prior to undergoing any study-specific procedures.

After determination that all inclusion/exclusion criteria have been met, enrolled subjects will receive the LipiFlow system treatment on both eyes. The investigator or designee will complete a questionnaire regarding the clinical use of Activators LFD-2100 for each subject (see **Appendix A**).

VISIT PROCEDURES:

- 1) Informed consent.
- 2) Screening and enrollment.
- 3) Perform a pre-treatment slit lamp evaluation, non-dilated fundus exam, ocular surface staining for all the subjects, and optional meibomian gland assessment at the investigator's discretion.

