11. ADVERSE EVENTS AND PRODUCT COMPLAINTS

11.1 DEFINITIONS

Adverse Event (AE)

An adverse event is defined (following ISO 14155) as any untoward medical occurrence, unintended disease or injury, or untoward clinical signs (including abnormal laboratory findings) in subjects, users or other persons, whether or not related to the study device.

Serious Adverse Event (SAE)

An adverse event is considered serious (following ISO 14155) if it is an untoward occurrence which may or may not be related to use of the study device that

- is sight- or life-threatening,
- results in death,
- requires inpatient hospitalization or prolongation of hospitalization (a planned hospitalization for a pre-existing condition without a serious deterioration in health is not considered a serious adverse event),
- results in permanent impairment of a body structure or body function,
- necessitates medical or surgical intervention to prevent permanent impairment to a body structure or function, or
- results in fetal distress, fetal death or a congenital abnormality or birth defect

Device-Related Adverse Event/Adverse Device Effect (ADE)

A device-related adverse event is defined as any adverse even that is believed to be definitely, probably or possibly related to the study device. A device-related event is also considered an adverse device effect (ADE; following ISO 14155) resulting from the use of the study device that may result from user error, insufficiencies or inadequacies in the instructions for use, deployment, implantation, installation, operation of any malfunction of the device.

Study-Specific Anticipated Adverse Events

The study specific anticipated AEs are listed below and will be classified as AE or SAE dependent upon its occurrence and severity during the course of the study:

- Eyelid/eye pain requiring discontinuation of the treatment procedure;
- Eyelid irritation or inflammation (e.g. edema, bruising, blood blister, dermatitis, hordeolum or chalazion);
- Ocular surface irritation or inflammation (e.g. corneal abrasion, conjunctival edema or conjunctival injection/hyperemia); and
- Ocular symptoms (e.g. burning, stinging, tearing, itching, discharge, redness, foreign body sensation, visual disturbance, sensitivity to light).

Study-Specific Serious Anticipated Adverse Events

There is no anticipated study-specific serious adverse event for this study.

Unanticipated Adverse Device Effect (UADE)/Unanticipated Serious Adverse Device Effect (USADE)

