11.3 ADVERSE EVENT AND COMPLAINT REPORTING REQUIREMENTS

All adverse events and any complaint encountered using any JJSV product, regardless of severity and whether or not attributed to the study device(s), are to be reported to JJSV and recorded on the case report form corresponding to the visit during which awareness of the event occurred. Adverse events are also to be reported to the reviewing IRB/IEC as per the IRB/IEC's reporting requirements. If required, adverse

events will be reported to the appropriate regulatory agencies according to all applicable laws and regulations.

Reporting of adverse events shall follow the applicable Regulations. General guidelines are provided below:

Adverse Event Reporting

An adverse event that is not serious or device-related is to be reported to JJSV in a timely manner. Notification of non-serious and non-device related adverse events will occur by recording events on the CRF when noted. Such adverse events are also to be reported to the reviewing IRB/IEC per their reporting requirements.

Complaints/Device Deficiency Reporting

A general product complaint or device deficiency is to be reported to JJSV in a timely manner. Notification of complaints/device deficiencies will occur by either recording complaints on the CRF when the complaint occurred (e.g. operative form) or by a phone call to the Sponsor. Any device deficiency that could have led to a serious adverse event without suitable action or intervention, or under less fortunate circumstances, must be reported to the sponsor immediately (no later than 24 hours after detection). Device deficiencies that could have led to a serious adverse event should also be reported to the investigator's IRB/IEC per their reporting requirements.

Serious and/or Device-Related Adverse Event Reporting

Serious and/or device related events (ADEs) are to be documented using the Serious Adverse Event/Adverse Device Effect (SAE/ADE) CRF. In the event of a serious adverse event (SAE), which may or may not be related to use of the study device, JJSV must be notified immediately (no later than 24 hours after detection). Any SAE is to be reported by phone (and/or email) and by submitting the completed SAE/ADE CRF. Any SAE or device-related AE should also be reported to the investigator's IRB/IEC per their reporting requirements.

Unanticipated Adverse Device Effect (UADE)/Unanticipated Serious Adverse Device Effect (USADE) Reporting

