20.2 STUDY ENDPOINTS

Primary Endpoint:

- Successful completion of LipiFlow treatment with Activator LFD-2100 in 95% or more cases.

The treatment reports automatically generated by LipiFlow Console after completion of each treatment will show if the treatment completion is successful. The frequency and proportion of successful completion of treatment will be reported. The expected proportion of successful completion of LipiFlow treatment question will be greater than or equal to 95%.

Other Endpoints:

- Questionnaire rating of each step in the LipiFlow treatment procedure with Activator LFD-2100.

For questions with a 'Yes' or 'No' response, the frequency and proportion of each question with response 'Yes' will be reported. For questions with five levels of

rating score responses, the frequency and proportion of each level of rating score responses will be tabulated. The mean and median of rating score of each question will also be reported.

- Rate of adverse events and complications.

The type and rates of adverse events will be summarized.

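### The SAP counts adverse events only by eye, so non-ocular and user events have no correct place in the table and the number of subjects affected is not shown

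*SAP*

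**What the plan says.** **Analysis.** SAP 4.2.4 gives one rule for adverse events: "The frequency and proportion of eyes with complications and adverse events will be reported throughout the study". SAP Appendix I repeats it as a single row of counts and percentages with eyes in the unit column. The only rows with subjects as the unit are enrollment and demographics. The SAP plans listings of eyes for unsuccessful treatments (4.1) and for low questionnaire ratings (4.2.1), but none for adverse events.

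**Definition and collection.** Protocol 11.1 takes adverse events to be untoward occurrences "in subjects, users or other persons, whether or not related to the study device". Its criteria for a serious event include death, fetal outcomes and an event that "requires inpatient hospitalization or prolongation of hospitalization". Protocol 11.3 has every adverse event reported and recorded, whatever its severity or cause.

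**Protocol analysis text.** Protocol 20.2 says only "The type and rates of adverse events will be summarized" and names no unit.

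**Design.** According to the protocol synopsis, "enrolled subjects will receive the LipiFlow system treatment on both eyes", and the size is given in eyes: "Minimum 50 eyes and up to 100 eyes to be treated".

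**The concern.** Two things go wrong when the eye is the only unit.

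First, some events that the protocol collects do not belong to an eye. A hospitalization, a systemic reaction or an injury to the operator has neither a natural numerator nor a natural denominator in a table of eyes. The SAP does not say how to count such an event, so it could be left out, put against one eye or put against both, and two programmers could produce different tables from the same data.

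Second, the eyes come in pairs. The same eye count can arise from one person with both eyes affected or from two people with one eye each. Someone judging the tolerability of the new Activator will want to know what share of treated people had an event, and the planned table cannot answer that.

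At stake is how completely and clearly the safety results are reported. No planned test or decision depends on this table.

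**Working it through.** **The plan's own figure.** Neither document states a rate, interval or precision for adverse events, so there is none to reproduce. The only computed figure in the SAP (section 5) concerns treatment completion: 1.96 × √(0.95 × 0.05 / 50) = 0.060, which gives 89% to 101%, cut at 100%. It has no bearing on adverse events.

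**Inputs.**
- Eyes treated: 50 to 100 (protocol synopsis; SAP 1).
- Eyes per subject: 2 (protocol synopsis and 10.1).
- Treated subjects, S: 50/2 = 25 to 100/2 = 50, if every subject is treated in both eyes as planned.
- Event counts are illustrative, since the documents give no expected rate.

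**Step 1: eye rate against subject rate for ocular events.** Let b subjects have an event in both eyes and u subjects have one in a single eye.
- Eye rate = (2b + u) / (2S)
- Subject rate = (b + u) / S
- Ratio of eye rate to subject rate = (2b + u) / (2b + 2u). This is 1/2 when all events are unilateral (b = 0) and 1 when all are bilateral (u = 0).

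| S | b | u | Eye rate | Subject rate |
|---|---|---|---|---|
| 25 | 0 | 2 | 2/50 = 4% | 2/25 = 8% |
| 25 | 1 | 0 | 2/50 = 4% | 1/25 = 4% |
| 25 | 2 | 0 | 4/50 = 8% | 2/25 = 8% |
| 50 | 0 | 2 | 2/100 = 2% | 2/50 = 4% |
| 50 | 1 | 0 | 2/100 = 2% | 1/50 = 2% |

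Rows 1 and 2 look the same in the planned table but differ twofold in the share of subjects affected. So do rows 4 and 5.

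**Step 2: one non-ocular event in one subject.** By subject this is 1/25 = 4% at the minimum size, or 1/50 = 2% at the maximum. In a table of 50 eyes it could appear as 0/50 = 0%, 1/50 = 2% or 2/50 = 4%, depending on a convention that the SAP does not give. With 100 eyes the three results are 0%, 1% and 2%.

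**Step 3: an event in a user.** Protocol 11.1 counts it as an adverse event, but the user contributes no treated eye and is not a study subject. No entry in a table of eyes, or of subjects, would be correct.

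**Step 4: does another planned output recover these events?** The other safety-related rows of SAP Appendix I (staining, slit-lamp findings and ocular symptoms) are all by eye. There is no adverse event listing and no subject-level row. Protocol 20.2 is not limited to eyes, but it names no unit and specifies no table.

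**The case against.** The best case for the plan has four parts.

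- **The eye is a sensible unit here.** One Activator is used per eye (protocol 10.4), and every anticipated event listed in protocol 11.1 concerns the eye or eyelid. This stands, and it is why the eye table should stay. It does not show how many people were affected.
- **Few non-ocular events are likely.** There are one or two visits, exams and treatment take about one to two hours, and no serious event is anticipated. This also stands, and it limits the severity. A rare serious event is still one that a safety table has to be able to show.
- **Nothing escapes oversight.** Serious and device-related events go on a dedicated form and to the sponsor and ethics board (protocol 11.3), and the medical monitor reviews them (15.3). A reader might infer from the eye-only table that such an event would go unnoticed. The documents do not support that. The gap is in the planned analysis, not in collection or monitoring.
- **Protocol 20.2 promises a summary of types and rates without restricting it to eyes.** That is true, and the SAP does not withdraw it. But the SAP is where the unit is fixed, and the only unit it fixes is the eye.

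A reader might also infer that the plan overstates the precision of its safety result by treating paired eyes as independent. The documents do not support this: only counts and percentages are planned for adverse events, with no interval, test or stated precision. Upper confidence limits for zero events on 50 eyes and on 25 subjects would also compare two different quantities, risk per eye and risk per subject. The between-eye correlation needed to express a loss of information is not given. Nor do bilateral events inflate the reported percentage: 4/50 and 2/25 are both 8%.

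**Conclusion.** The point holds as a gap in the planned safety reporting, of minor to moderate severity. The SAP states one unit for adverse events, and that unit does not fit all the events the protocol defines and collects. For ocular events, the eye rate lies between half the subject rate and the full subject rate, and the planned table does not show where. With two unilateral events this means 4% of eyes against 8% of subjects at the minimum size, and 2% against 4% at the maximum.

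These figures assume that every subject is treated in both eyes, as planned, and the event counts are examples rather than expected values. No planned inference is invalidated, and adverse events are among the other endpoints, not the primary one.

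**What to change.** In SAP 4.2.4 and Appendix I:

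1. Keep the table by eye, and label it as ocular adverse events.
2. Add the number and percentage of treated subjects with at least one adverse event.
3. Report non-ocular adverse events and all serious adverse events by subject, with treated subjects as the denominator.
4. List events in users or other persons separately, without a rate. With three to five operators (protocol 10.1), a percentage would mean little.
5. If a confidence interval is ever added, base it on subjects.

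The cost is a few table rows and one listing. Protocol 11.3 already requires the events to be recorded, so conduct and sample size do not change. The case report form is not among the documents, so the sponsor should check that it records which eye or eyes were affected, whether the event was non-ocular, and whether it happened to a subject or to someone else.
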